Appendix E: Criteria for Threshold Analysis

Table 12-3 Threshold Analysis Criteria for Laboratory Tests (as applicable)

Parameter	Threshold Analysis	Comments
Clinical Chemistry (LFT)		
ALT	>ULN - ≤3xULN >3x - ≤ 5xULN >5x - ≤ 8xULN >8x - ≤ 20xULN >20xULN	FDA DILI Guidance Jul 2009.
AST	>ULN - ≤3xULN >3x - ≤ 5xULN >5x - ≤ 8xULN >8x - ≤ 20xULN >20xULN	FDA DILI Guidance Jul 2009.
ALT or AST	(ALT>ULN - ≤ 3xULN) or (AST>ULN - ≤ 3xULN) (ALT>3x - ≤ 5xULN) or (AST>3x - ≤ 5xULN) (ALT>5x - ≤ 8xULN) or (AST>5x - ≤ 8xULN) (ALT>8x - ≤ 20xULN) or (AST>8x - ≤ 20xULN) ALT>20xULN or AST> 20xULN	FDA DILI Guidance
Alkaline Phosphatase	>ULN - ≤ 1.5xULN >1.5x - ≤ 2.5xULN >2.5x - ≤ 5xULN >5x - ≤ 20xULN >20xULN	FDA DILI Guidance Jul 2009.
Total Bilirubin	>ULN - ≤ 1.5xULN >1.5x - ≤ 2xULN >2x - ≤ 3xULN >3x - ≤ 10xULN >10xULN	FDA DILI Guidance Jul 2009.
Direct Bilirubin	>ULN - ≤ 1.5xULN >1.5x - ≤ 2xULN >2x - ≤ 3xULN >3x - ≤ 10xULN >10xULN	FDA DILI Guidance Jul 2009.
Indirect Bilirubin	>ULN - ≤ 1.5xULN >1.5x - ≤ 2xULN >2x - ≤ 3xULN >3x - ≤ 10xULN >10xULN	FDA DILI Guidance Jul 2009.
ALT and Total Bilirubin	ALT>3xULN and TBILI>2xULN	FDA DILI Guidance Jul 2009.
AST and Total Bilirubin	AST>3xULN and TBILI>2xULN	FDA DILI Guidance Jul 2009.

Table 12-3 Threshold Analysis Criteria for Laboratory Tests (as applicable)

Parameter	Threshold Analysis	Comments
(ALT or AST) and Total Bilirubin	(ALT>3xULN or AST>3xULN) and TBILI>2xULN	FDA DILI Guidance Jul 2009.
GGT	>ULN - ≤ 2.5xULN >2.5x - ≤ 5xULN >5x - ≤ 20xULN >20xULN	CTCAE grade 1-4
Clinical Chemistry (NON-LFT)		
Albumin	<LLN - ≥ 30 g/L <30 - ≥ 20 g/L <20 g/L	CTCAE grade 1-3
Amylase	>1x - ≤ 1.5xULN >1.5x - ≤ 2xULN >2x - ≤ 5xULN >5xULN	Criteria based upon CTCAE
Creatinine	>ULN - ≤ 1.5xULN >1.5x - ≤ 3xULN >3x - ≤ 6xULN >6xULN	CTCAE grades 1-4
Lipase	>ULN - ≤ 1.5xULN >1.5x - ≤ 2xULN >2x - ≤ 5xULN >5xULN	Criteria based upon CTCAE
Total protein	<LLN >ULN	No CTCAE
Creatine kinase	>ULN - ≤ 2.5xULN >2.5x - ≤ 5xULN >5x - ≤ 10xULN >10xULN	CTCAE grades 1-4
Hematology		
Hemoglobin	Hgb decreased (anemia) <LLN - ≥ 100 g/L <100 - ≥ 80 g/L < 80 g/L	CTCAE grade 1-3
	Hgb increased >ULN - ≤ 20 g/L above ULN >20 g/L above ULN - ≤ 40 g/L above ULN >40 g/L above ULN	CTCAE grade 1-3
Platelets	Platelet decreased <LLN - ≥ 75 x 10e9 /L <75 - ≥ 50 x 10e9 /L <50 - ≥ 25 x 10e9 /L <25 x 10e9 /L	CTCAE grade 1-4
	Platelet increased >ULN	No CTCAE available

Table 12-3 Threshold Analysis Criteria for Laboratory Tests (as applicable)

Parameter	Threshold Analysis	Comments
Reticulocytes/Erythrocytes (%)	<LLN >ULN	No CTCAE
Coagulation		
Activated partial thromboplastin time (PTT)	>ULN - $\leq 1.5 \times \text{ULN}$ >1.5x - $\leq 2.5 \times \text{ULN}$ >2.5xULN	CTCAE grade 1-3
Prothrombin time (PT) International Normalized Ratio (INR)	>ULN - $\leq 1.5 \times \text{ULN}$ >1.5x - $\leq 2.5 \times \text{ULN}$ >2.5xULN	CTCAE grade 1-3

Table 12-4 Threshold Analysis Criteria for ECGs

Parameter	Threshold Analysis	Comments
HR	Bradycardia ≤ 50 bpm	
	Tachycardia ≥ 140 bpm	
PR	≥ 200 ms and increase from baseline ≥ 20 ms	
QRS	≥ 120 ms	
QTc	Absolute values (ms) >450 ms (Male) or >470 ms (Female) ≥ 500 ms	To be applied to any kind of QT correction formula.
	Increase from baseline Increase from baseline 30-60 ms Increase from baseline >60 ms	

Table 12-5 Threshold Analysis Criteria for Vital Signs

Parameter	Threshold Analysis	Comments
Pulse Rate	Same as above in ECG category	
SBP	>120 mmHg < 70 mmHg	
DBP	>80 mmHg <50 mmHg	
Weight	Weight gain ≥ 5 % increase from baseline	CTCAE grade 1-3
	Weight loss ≥ 5 % decrease from baseline	CTCAE grade 1-3

Table 12-6 Threshold Analysis Criteria for Laboratory Tests

Parameter	Threshold Analysis	Comments
Clinical Chemistry (LFT)		
ALT or AST	>3xULN	
	>5xULN	
	>8xULN	

Appendix F: Adverse Events of Special Interest

Table 12-3 MedDRA Preferred Terms for Event of Special Interest	
Adverse event of special interest	MedDRA preferred terms
Elevated transaminases	Alanine aminotransferase abnormal, Alanine aminotransferase increased, Aspartate aminotransferase abnormal, Aspartate aminotransferase increased, Transaminases abnormal, Transaminases increased, Liver function test abnormal, Liver function test increased, Hypertransaminasaemia, Hepatic enzyme abnormal, Hepatic enzyme increased
Rash	Rash, Rash erythematous, Rash macular, Rash maculo-papular, Rash maculovesicular, Rash vesicular, Rash pruritic, Rash follicular, Rash pustular, Nodular rash, Drug eruption, Fixed eruption, Urticaria, Urticaria papular, Urticaria vesiculosa, Urticarial dermatitis, Rash morbilliform, Rash papular, Rash papulosquamous, Rash rubelliform, Rash scarlatiniform , Drug hypersensitivity, Type IV hypersensitivity reaction, Dermatitis, Dermatitis atopic, Epidermolysis, Skin toxicity, Dermatitis allergic, Dermatitis exfoliative, Dermatitis exfoliative generalised, Erythema multiforme, Exfoliative rash, Mucocutaneous rash, Acute generalised exanthematous pustulosis, Cutaneous vasculitis, Urticarial vasculitis, Dermatitis bullous, Drug reaction with eosinophilia and systemic symptoms, Epidermal necrosis, Oculomucocutaneous syndrome, Skin exfoliation, Skin necrosis, Stevens-Johnson syndrome, Toxic epidermal necrolysis, Toxic skin eruption, Perioral dermatitis, Vasculitic rash, Immune-mediated dermatitis, Penile rash, SJS-TEN overlap, Erythrodermic atopic dermatitis, Scrotal dermatitis, Anal Rash, generalised bullous fixed drug eruption

Note: the preferred terms listed in the table is based on the MedDRA version applicable at the time of finalization of the SAP. If the MedDRA version is upgraded at the time of the analysis, the corresponding preferred terms based on the upgraded version, including adding, removing and renaming the preferred terms, will be used in the analysis of adverse events of special interest.

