13.1.1.2 Clinically Significant Assessments

Study assessments including laboratory tests, ECGs, PEs, and vital signs will be assessed and those deemed to have clinically significant worsening from baseline will be documented as an AE. When possible, a clinical diagnosis for the study assessment will be provided, rather than the abnormal test result alone (e.g., urinary tract infection, anemia). In the absence of a diagnosis, the abnormal study assessment itself will be listed as the AE (e.g., bacteria in urine or decreased hemoglobin).

An abnormal study assessment is considered clinically significant if the subject has 1 or more of the following:

- Concomitant signs or symptoms related to the abnormal study assessment
- Further diagnostic testing or medical/surgical intervention
- A change in the dose of study drug or discontinuation from the study

Repeat testing to determine whether the result is abnormal, in the absence of any of the above criteria, does not necessarily meet clinically significant criteria. The determination of whether the study assessment results are clinically significant will be made by the investigator.

A laboratory value that is Grade 4 will not automatically be an SAE. A Grade 4 laboratory value will be an SAE if the subject's clinical status indicates a life-threatening AE.

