13.1.1.3 Documentation of Adverse Events

All AEs will be collected from the time the ICF is signed until the subject completes study participation, as defined in Section 9.1.6.

All subjects will be queried, using nonleading questions, about the occurrence of AEs at each study visit. When possible, a constellation of signs and/or symptoms will be identified as 1 overall event or diagnosis. All AEs for enrolled subjects will be recorded in the CRF and source document. AEs for subjects who are screened but not subsequently enrolled will be recorded only in the subject's source documents. The following data will be documented for each AE:

- Description of the event

- Classification of “serious” or “nonserious”
- Date of first occurrence and date of resolution (if applicable)
- Severity
- Causal relationship to study drug(s)
- Action taken
- Outcome
- Concomitant medication or other treatment given

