9.4.1.1 Adverse Events of Special Interest

For this study, elevated transaminase events and rash events, as determined by MedDRA preferred terms in [Appendix F](#), are considered as adverse events of special interest.

For treatment-emergent elevated transaminase events and rash events, the following categories will be summarized by treatment group:

- Subjects with events

- Subjects with events by maximum severity
- Subjects with events leading to treatment discontinuation
- Subjects with events leading to treatment interruption
- Subjects with serious events
- Subjects with related serious events
- Subjects with events leading to death
- Duration of events
- Time-to-onset of first event

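### A transaminase elevation recorded only as a liver diagnosis can be left out of the special-interest summary, because SAP Appendix F lists laboratory-type terms only

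*SAP*

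**What the plan says.** SAP 9.4.1.1 names two categories of special interest, "elevated transaminase events and rash events, as determined by MedDRA preferred terms in" Appendix F. Membership of the list is the only entry route: no laboratory value, system organ class or medical review can add a case. The note under the Appendix F table lets the list change only to follow a MedDRA version upgrade.

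The row for elevated transaminases begins "Alanine aminotransferase abnormal, Alanine aminotransferase increased, Aspartate aminotransferase abnormal, Aspartate aminotransferase increased, Transaminases abnormal, Transaminases increased" and ends "Liver function test abnormal, Liver function test increased, Hypertransaminasaemia, Hepatic enzyme abnormal, Hepatic enzyme increased".

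The recording rules are in the protocol. For abnormal assessments judged clinically significant, section 13.1.1.2 says that, when possible, "a clinical diagnosis for the study assessment will be provided, rather than the abnormal test result alone". It then gives the fallback: "In the absence of a diagnosis, the abnormal study assessment itself will be listed as the AE". Section 13.1.1.3 adds that, again when possible, "a constellation of signs and/or symptoms will be identified as 1 overall event or diagnosis".

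**The concern.** The recording rule and the counting rule pull in different directions. The protocol prefers a diagnosis as the event term where one exists. The SAP counts only events whose term is a test result. A child with raised ALT whose event is entered solely as hepatitis or drug-induced liver injury has followed the protocol and is not counted.

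This matters because the summary is more than a tally of raised enzymes. It has rows for maximum severity, interruption, discontinuation, seriousness and related seriousness, down to "Subjects with events leading to death". Protocol 13.1.1.2 says a Grade 4 laboratory value is not a serious event by itself, and that it becomes one when the subject's clinical state indicates a life-threatening event. The serious rows may therefore depend partly on clinically apparent illness, which can carry a diagnosis. A reader of the study report could take a zero in such a row as a statement about elevated-transaminase events in general, when it speaks only for events entered under 11 laboratory-type terms.

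The rash row of the same table is built differently. Alongside descriptive rash terms it includes diagnoses such as "Stevens-Johnson syndrome, Toxic epidermal necrolysis, Toxic skin eruption". The SAP does not explain the difference.

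**Working it through.** The plan states no figure to reproduce; the check is mainly a comparison of text.

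**Step 1: classify the terms.** Six terms cover ALT, AST and transaminases, each as abnormal or increased. Four cover liver function test and hepatic enzyme, each as abnormal or increased. One is hypertransaminasaemia, which also names only a raised enzyme level. Total: 6 + 4 + 1 = 11 laboratory-type terms and 0 liver diagnoses.

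**Step 2: follow each way an elevation can be recorded as an adverse event.**

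| How the site records it | Allowed by protocol 13.1.1.2 and 13.1.1.3? | Matches Appendix F? |
|---|---|---|
| Laboratory finding, no diagnosis available | Yes, as the fallback | Yes, counted |
| Diagnosis and laboratory finding, as two events | Not excluded | Yes, through the laboratory term |
| Diagnosis only | Yes, in line with the stated preference | No, absent from every row |

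Only the third route leads to omission.

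**Step 3: see what other outputs recover.**

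| Item in the special-interest summary | Available elsewhere for a diagnosis-only event? |
|---|---|
| Seriousness, related seriousness, interruption, discontinuation, maximum severity, death | Yes, by arm under its own preferred term (SAP 9.4.1 tables); listings also cover interruptions, discontinuations, Grade 3/4 events, serious events and deaths |
| Size of the enzyme rise, with or without raised bilirubin | Yes, from laboratory data whatever the event term (SAP 9.4.2 and Appendix E) |
| One grouped count of subjects with a transaminase-related event | No |
| Duration and time to first onset for the group | No; start and resolution dates are collected for each event (protocol 13.1.1.3), but these two summaries are specified only in SAP 9.4.1.1 |

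**Step 4: size.** The planned number per arm is 108 / 2 = 54 (protocol 12.1, 1:1 randomization). One subject is 1 / 54 = 0.0185, or about 1.9 percentage points. If an arm's only serious or treatment-stopping transaminase event were recorded as a diagnosis alone, that row would show 0/54 instead of 1/54. The documents do not say what share of such events is recorded only as a diagnosis; the possible range runs from none to all of those for which a diagnosis was reached.

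**The case against.** The case on the other side has five parts.

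- **The list fits its label.** The category is elevated transaminases, not liver injury, and the SAP nowhere claims that it captures all hepatic events. This is true, but it does not answer the point: a child with raised ALT recorded as hepatitis does have elevated transaminases and is still not counted.
- **The protocol wording is soft.** The preference for a diagnosis applies when possible, and the comparison is with the test result alone, so recording both is open to the site. This stands. The conclusion can only be that events may be left out, not that they will be.
- **The information is elsewhere.** SAP 9.4.1 and 9.4.2 report nearly all of it by arm. This stands too and limits the point to the grouped count, duration and onset, and to how a reader interprets the rows of this one table.
- **Rash is not a fair comparison.** Rash has no parallel laboratory data set, so its event terms must carry the whole signal, whereas transaminases have a full threshold analysis. This largely stands. The contrast shows a difference in construction; it is not proof of an error.
- **A wider list lets in other causes.** Protocol 9.8.1 itself gives viral hepatitis as an example of an alternative etiology. This is a real cost, and the fix has to keep such events separable.

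A reader might go further and infer that the most serious liver events disappear, that an event is more likely to be missing the more severe it is, or that the comparison with placebo for serious liver events is pulled toward no difference. The documents do not support these readings. They give no figure linking severity to the way an event is recorded. Serious, treatment-stopping and fatal events are tabulated by arm under any preferred term. The same list applies to both arms of a double-blind trial, so the direction of any effect on the between-arm difference depends on events not yet seen.

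**Conclusion.** The concern holds in a limited form. As written, a transaminase elevation recorded only as a diagnosis can be omitted from all rows of the special-interest summary. The consequence is a possible undercount in one descriptive grouped safety table. The events and their laboratory values remain visible by arm in other outputs, SAP 9.4 plans no statistical testing of safety, and the primary analysis is untouched.

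Each omitted event is worth about 1.9 percentage points of an arm. That assumes 54 treated subjects per arm in the Safety Set and an event with no separately recorded laboratory term. How many events will be affected cannot be estimated from the documents and may be none. The change is still worth making: it is cheap, and it stops a zero in the serious, discontinuation or death row from being read as more than it is.

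**What to change.** In SAP 9.4.1.1 and Appendix F:

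1. Keep the present 11-term count as its own row, labelled as based on laboratory-type terms.
2. For each category in 9.4.1.1, add a row that also counts treatment-emergent hepatic diagnosis events in subjects with treatment-emergent ALT or AST >3×ULN. That cut-off is already in the Appendix E threshold table for ALT or AST. List the diagnosis terms in Appendix F before unblinding.
3. Add a cross-reference to the system organ class and preferred term tables and listings in 9.4.1, and to the liver outputs in 9.4.2 and Appendix E.

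Tying the added row to a measured elevation keeps it within the transaminase category. Diagnoses without such an elevation stay in the general tables.

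The cost is SAP wording and one reprogrammed table. SAP section 4 allows revision by amendment before database lock and unblinding. No new data collection is needed. The small downside is that the added row may include liver events with another identified cause; the retained 11-term row keeps the narrower count separate.
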